#### 1.2 Current Standard of Care

One particular area with a specific need for new therapeutic options is stage III NSCLC, especially for patients with unresectable or inoperable tumors. The five-year OS for patients with stage IIIA and IIIB NSCLC are 14% and 5% respectively (3). Previous efforts to improve outcomes in this population have not changed the landscape of treatment significantly in the last few decades. Until the 1980s, radiotherapy alone was the standard of care for patients with locally or regionally advanced NSCLC. Five-year survival rates for radiotherapy alone were only 3-10% (4). Because of these poor outcomes, trials looking at sequential chemoradiation were completed showing an advantage in OS for the addition of chemotherapy (4, 5). Following this, sequential chemoradiation was compared to concurrent chemoradiation showing a subsequent improvement in OS for concurrent therapy (6, 7). This finding was confirmed in a meta-analysis showing an absolute benefit of 4.5% at five years favoring concurrent chemoradiation over sequential (8). Since that time, a number of subsequent trials evaluating induction (9, 10) and consolidation (10-14) chemotherapy have failed to demonstrate an improvement in OS in this population. Recently, a trial was completed which gave patients with unresectable stage III NSCLC concurrent chemoradiation followed by either 12 months of consolidation Durvalumab (PD-L1 inhibitor) or placebo. This trial showed an improved median PFS of 17.2 months with durvalumab vs. 5.6 months with placebo (HR 0.51). Overall survival also favored the Durvalumab arm with a 24-month OS of 66.3% vs. 55.6% in the placebo arm (HR 0.68, p=0.0025) (15). Based on this data, consolidation Durvalumab should be considered a potential new standard of care following chemoradiation for patients with unresectable stage III NSCLC.

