#### 6.2 Subject Withdrawal/Discontinuation Criteria

Subjects may withdraw consent at any time for any reason or be withdrawn from the trial at the discretion of the site investigator should any untoward effect occur. In addition, a subject may be withdrawn by the sponsor-investigator or BTCRC if enrollment into the trial is inappropriate, the trial plan is violated, or for administrative and/or other safety reasons. Specific details regarding discontinuation or withdrawal are provided below.

A subject must be discontinued from the trial treatment for any of the following reasons:

- Confirmed radiographic disease progression by RECIST 1.1 criteria
- Unacceptable adverse experiences as described in Section 5.3 and 11.1

- Intercurrent illness that prevents further administration of treatment
- Site investigator's decision to withdraw the subject
- A female subject has a confirmed positive serum/urine pregnancy test
- Noncompliance with trial treatment or procedure requirements
- Completed 6 months of treatment with protocol therapy
- Subject refuses further treatment
- If a subject has a treatment delay of more than 12 weeks from last infusion. See section 6.1.

A subject must be discontinued from the trial for any of the following reasons:

- Administrative reasons
- The subject or legal representative (such as a parent or legal guardian) withdraws consent.
- The subject is lost to follow-up

The End of Treatment and Follow-up visit procedures are listed in Section 7 (Study Schedule of Events and Visit Requirements). After the end of treatment, each subject will be followed for 100 days for adverse event monitoring (serious adverse events will be collected for 100 days after the end of treatment as described in Section 12.2.2). Subjects who discontinue for reasons other than progressive disease will have post-treatment follow-up for disease status until disease progression, initiating a non-study cancer treatment, withdrawing consent or becoming lost to follow-up. After documented disease progression each subject will be followed for survival for up to 2 years, withdrawal of consent, or the end of the study, whichever occurs first.

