- 10. Screening scan including at least CT portion of the chest and abdomen must be performed within 56 days after the completion of chemoradiation or consolidation. PET CT may be done in place of regular CT scans at the discretion of the site investigator. Baseline scans should be done within 28 days prior to treatment initiation. Radiographic disease assessment will be done every 12 weeks ± 4 weeks during study treatment. The scan interval may be reset if scans were done early for clinical reasons. See also 8.3.
- 11. After completion of protocol therapy, subjects who discontinue for reasons other than progressive disease will have post-treatment follow-up for disease status until disease progression, initiating a non-study cancer treatment, withdrawing consent or becoming lost to follow-up. Post treatment radiographic disease assessment should be performed every 3 months until progression. After documented disease progression each subject will be followed for survival every 3 months for up to 2 years, withdrawal of consent, or the end of the study (whichever occurs first).
- 12. A head MRI or CT should be done prior to study treatment for subjects that are symptomatic or have not had prior brain imaging.
- 13. For subjects who meet all eligibility criteria and have recovered sufficiently from treatment with chemoradiation, initial consolidation therapy with nivolumab will be started within 56 days after chemoradiation is complete. For subjects who meet all eligibility criteria after completion of up to two consolidation chemotherapy treatments, therapy with nivolumab will be started within 56 days after last cycle of chemotherapy.
- 14. Mandatory submission of unstained slides from an archived tumor block (if available) for PD-L1, CD4, CD8 by IHC. In addition, whole exome sequencing, RNA sequencing, methylation analysis will be performed. See Correlative Laboratory Manual (CLM) for collection, labeling and shipping instructions.
- 15. Mandatory blood samples for correlative testing should be drawn pre-treatment on C1D1, C2D1 and either at the End of Treatment Visit or if the subject develops any grade 3-4 pneumonitis. See CLM for collection, labeling, and shipping instructions.
- 16. If subject has a bronchoscopy with BAL for clinical reasons, please collect a portion of the of BAL fluid for correlative analysis (optional).

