## 8.5 Long Term Follow-up Evaluations

After completion of protocol therapy, subjects who discontinue for reasons other than progressive disease will have post-treatment follow-up for disease status until disease progression, initiating a non-study cancer treatment, withdrawing consent or becoming lost to follow-up. After documented disease progression each subject will be followed for survival every 3 months ( $\pm$  4 weeks) for up to 2 years, withdrawal of consent, or the end of the study (whichever occurs first).

• Treatment-related adverse events will be followed until resolution, return to baseline, or deemed clinically insignificant. Adverse events (from time of consent) and concomitant medications (28 days prior to start of protocol treatment) should be assessed and recorded until 100 days after last

dose of study drug or until a new anti-cancer treatment starts, whichever is earlier. SAE's and the conmeds used to treat them will be collected up to 100 days post treatment.

• For subjects who discontinue for reasons other than progressive disease, radiographic disease assessment should be performed every 3 months for up to 2 years until progression, initiating a non-study cancer treatment, withdrawing consent or becoming lost to follow-up. The scan interval may be reset if scans were done sooner for clinical reasons. PET CT may be done in place of regular CT scans at the discretion of the site investigator. This imaging may be done locally. Once patients are off treatment and on follow-up, the window for imaging is ±4 weeks.

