## 13.3 Sample Size and Accrual

This is a non-comparative two-arm trial with each arm being analyzed separately. For Arm 1, when the sample size is 51, a non-parametric test (single-group and based on a non-parametric estimate of the cumulative hazard function) with a one-sided 0.10 significance level will have 80% power to detect an 18 month PFS rate of 44% relative to a historical control rate of 30% (similar to the PACIFIC trial) assuming an accrual period of approximately 24 months and maximum follow-up of 48 months (i.e. would allow for up to 24 months of follow-up after accrual ends). For Arm 2, when the sample size is 48, a non-parametric test (as above) with a one-sided 0.10 significance level will have 80% power to detect an 18 month PFS of 59% relative to a historical control rate of 44% (similar to the PACIFIC trial in the checkpoint inhibitor arm and a 15% increase in absolute magnitude) assuming an accrual period of approximately 24 months. To account for non-evaluable subjects (5%), 54 subjects will be enrolled in Arm 1 and 51 subjects in Arm 2.

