## 13.7.2 Analysis Plans for Secondary Objectives

OS will be estimated using a Kaplan-Meier curve and 95% confidence intervals for the OS medians in the randomized population. The cumulative incidence for time to metastatic disease will be calculated with those dying from causes other than metastatic disease as a competing risk, and right censoring for patients alive and without metastases. Safety will be assessed in the Safety population. Separate frequency tables will be generated for each arm.

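### Survival contact ends 2 years after progression, so OS censoring after month 24 depends on disease course and biases the planned median OS and late curve, usually but not always upward

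*Combined protocol and SAP*

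**What the plan says.** Section 6.2 states "After documented disease progression each subject will be followed for survival for up to 2 years", with the alternative ends "withdrawal of consent, or the end of the study, whichever occurs first". Footnote 11 of the Arm 1 calendar has "After documented disease progression each subject will be followed for survival every 3 months for up to 2 years", the Arm 2 footnote matches it, and 8.5 has the same 2-year limit.

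For subjects who stop treatment without progression, 6.2 provides "post-treatment follow-up for disease status until disease progression, initiating a non-study cancer treatment, withdrawing consent or becoming lost to follow-up". No time limit is attached there, in footnote 11 or in the first paragraph of 8.5. A later bullet in 8.5 does limit their imaging to 2 years. It does not say whether survival contact continues afterwards.

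The sample size in 13.3 is set "assuming an accrual period of approximately 24 months and maximum follow-up of 48 months". OS runs from randomization to death from any cause (2.2.2, 10.8.8). Section 13.7.2 plans a Kaplan-Meier curve and "95% confidence intervals for the OS medians in the randomized population". The plan gives no OS censoring rule, no sensitivity analysis for OS and no adjustment for dependent censoring.

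**The concern.** Kaplan-Meier treats a censored subject as having the same future risk as those still under observation. Censoring at study end meets that condition, because it depends only on entry date. The 2-year limit does not, because it removes living subjects at a time fixed by their own progression. From month 24 the risk set loses people who progressed long ago and keeps those who are progression-free or progressed recently. If these groups die at different rates, the curve is wrong from there on.

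At stake is a planned secondary estimate. The secondary objectives in 2.1.2 ask whether each arm improves OS relative to a historical control, and no concurrent control shares the distortion.

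**Working it through.** The plan states no OS median, OS power or OS precision, so there is no OS figure of its own to reproduce.

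**1. When the limit acts.** Let P be the month of progression and E the potential follow-up, 48 minus month of entry. With 24 months of accrual, E lies between 24 and 48. A progressed subject is censored alive at min(E, P + 24). For a subject entered at month 0:
- progression at month 3: censored at 3 + 24 = 27
- progression at month 20: censored at 20 + 24 = 44
- no progression: month 48, if survival contact continues

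Since P is above 0, nobody is censored by the limit before month 24, so the 24-month rate is untouched.

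**2. Where the median falls.** The only reference OS figures are in section 1.2: "24-month OS of 66.3% vs. 55.6% in the placebo arm". Both exceed 50%. If survival were exponential, the median would be 24 × ln 2 / (−ln S24):
- S24 = 0.663: 24 × 0.693 / 0.411 = 40.5 months
- S24 = 0.556: 24 × 0.693 / 0.587 = 28.3 months

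In simulated arms of 51 to 54 subjects the median fell after month 24, or was not reached, in 82-100% of trials.

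**3. Size if non-progressors stay at risk to study end.** Simulation with 400,000 subjects per setting. From the documents: 18-month PFS, 24-month OS, 24 months of accrual and study end at month 48. Assumed: uniform accrual, 10% of PFS events being deaths, Weibull PFS (shape 1.0 or 0.7), and Weibull post-progression survival (shape 0.8, 1.0 or 1.3) scaled to the 24-month OS. Examples at PFS 44% and OS 66.3%; the last row goes outside those shapes:

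| PFS shape / post-progression shape | Median OS, no limit → limit (months) | Later OS, no limit → limit |
|---|---|---|
| 1.0 / 1.0 | 34.5 → 35.3 (+0.8) | month 42: 0.400 → 0.423 (+2.3 points) |
| 0.7 / 1.3 | 35.0 → 38.0 (+3.0) | month 42: 0.415 → 0.466 (+5.1 points) |
| 1.0 / 0.5 (steeply falling hazard) | 39.4 → 39.0 (−0.4) | month 36: 0.531 → 0.529 (−0.2 points) |

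Ranges over the main shapes:
- PFS 44%, OS 66.3%: median +0.6 to +3.0 months; 36-month OS +0.7 to +3.2 points; 10-15% of subjects censored by the limit.
- PFS 30%, OS 55.6%: median 0 to +0.3 months; 36-month OS +0.4 to +3.3 points; up to 17% censored.

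With post-progression shape 0.5 included, the censored share reaches 19%. Without the limit, Kaplan-Meier recovers the true curve.

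**4. Wider assumptions.** A grid of 128 scenarios added:
- a front-loaded PFS shape, ln(ln 0.27 / ln 0.5) / ln(18 / 5.6) = 0.545, from the placebo median of 5.6 months (1.2) and 18-month PFS of 27% (1.4)
- a correlation of 0 or 0.4 between time to progression and survival after it
- 10% or 25% of PFS events being deaths
- an assumed 24-month OS of 72% for Arm 2

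Kaplan-Meier minus true OS was −0.3 to +1.9 points at month 30 and −1.0 to +4.3 at month 36. It was upward at month 36 in 118 of 128 scenarios. The exceptions had a falling post-progression hazard unrelated to time to progression. With front-loaded progression and OS of 66.3%, one median moved from 39.1 to 45.6 months (+6.5), and in some scenarios it was no longer reached. The censored share ran from about 3%, where few subjects live long after progression, to 19%.

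**5. At the planned size.** With n = 54, OS 66.3% and correlation 0.4, the median was reached in 82% of trials without the limit and 67% with it.

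**6. The other reading of 8.5.** Suppose survival contact with non-progressors stops at about month 30 (assumption: 6 months of treatment plus 24). With the post-progression limit also in place, at PFS 44% and OS 66.3%, 36-month OS is understated by about 4-6 points (for example 0.433 against a true 0.479) and the median by 1.0-4.2 months. Removing only the post-progression limit would then still leave 36-month OS 3.5-8 points too low.

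**The case against.** Four points can be made in the plan's defence.

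- **Direction.** A reader might infer that OS is certain to be overstated. The documents do not support that. The direction depends on the post-progression hazard, which they do not give, and on whether non-progressors remain under survival contact, which 8.5 leaves open. This objection stands, and the direction must be stated conditionally.
- **Noise.** At n = 54 the sampling SD of 36-month OS is 7-8 points, and the 95% sampling range of the median, where reached, is about 26-45 months at a 24-month OS of 66.3%. The bias is smaller than either. That limits its weight, but bias does not average out and it costs little to remove.
- **Use of OS.** A reader might infer that the historical comparison of OS is invalidated. Section 13.7.2 plans estimation only, with no OS test or benchmark. The only historical OS figures in the plan are 24-month rates, which the limit leaves intact. This also stands: the harm is confined to the median and the later curve.
- **Remedy.** Dropping the median altogether would discard usable data, given an error at month 30 of only −0.3 to +1.9 points. That is accepted.

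None of this removes the defect. The limit is stated consistently, and nothing in the analysis plan compensates for it.

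**Conclusion.** The concern holds in conditional form. Survival follow-up that ends 2 years after progression makes OS censoring after month 24 depend on disease course, and the planned Kaplan-Meier curve and median are biased there.

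If subjects without progression are followed to study end, the bias is usually upward, about 0 to 3 points at 36 months and 0 to 3 months in the median in the main settings. It can be larger if progression is strongly front-loaded, is negligible if the median lies near month 27-28, and can vanish or slightly reverse if the post-progression hazard falls steeply. If the imaging limit in 8.5 also ends survival contact, it mostly turns downward.

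These sizes rest on assumed survival shapes calibrated to the plan's reference rates. OS is a secondary endpoint, so this is a change that should be made and not a threat to the trial's main conclusion.

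**What to change.** In 6.2, 8.5 and footnote 11 of both calendars, delete the 2-year limit on survival follow-up. State that every subject, whether progressed, not progressed or started on non-study cancer treatment, is contacted for survival every 3 months until death, consent withdrawal or study end. The last group needs naming because its disease follow-up stops when the new treatment starts and no survival follow-up is then described. Say in 8.5 that the 2-year imaging limit does not end survival contact, and reconcile that limit with 6.2 and footnote 11, which have none. Add to 13.7.2 that subjects alive are censored for OS at the date last known alive.

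The cost is a minor amendment plus status calls or record checks for a minority of subjects up to the study end already planned, with no extra visits or scans.

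If the limit is kept, make the 24-month rate the main OS summary. Report the later curve and the median with numbers at risk, and with either a dependent-censoring caveat or a sensitivity analysis.

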#### 6.3 **Protocol Discontinuation**

If a subject decides to withdraw from the study (and not just from protocol therapy) all efforts should be made to complete the final study assessments. The site study team should contact the subject by telephone or through a clinic visit to determine the reason for the study withdrawal. If the reason for withdrawal is an adverse event, it will be recorded on the eCRF.

#### 7. ARM 1 (NIVOLUMAB): STUDY CALENDAR & EVALUATIONS

Cycle Length: Arm 1= 28 days	Screening		On Treatment Cycle 1+	Safety Follow up	Long Term Follow up 
	-28 d	-14 d	Day 1 (±3)	30 days (±7)	(±14 days)
REQUIRED ASSESSMENTS					
Informed Consent	Х				
Medical history (inc. NGS results, if done) and Height 		Х			
Physical examination including vital signs (BP, weight)		Х	Х	Х	
ECOG performance status		Х	Х	Х	
AEs & concomitant medications 		Х	Х	+30, +100	Х
Radiation Treatment Plan Data 			Х		
LABORATORY TESTING					
CBC with differential and platelet count		Х	$X^4$	Х	
Complete Metabolic Profile	Ì	Х	$X^4$	Х	
Direct bilirubin, Mg, Phos	Ì	Х	$X^4$	Х	
Creatinine clearance 		Х			
PT/INR and aPTT		Х			
Thyroid function (TSH, T3, T4) 		Х	C1  , Every odd cycle 		
ESR, CRP, vWF Ag and ferritin 			Pre C1, Pre C2	X 	
WOCBP: Serum or Urine pregnancy test, FSH (as needed) 		$-7d^{7}$			
DISEASE ASSESSMENT					
Pathology Report of diagnosis	X 				
CT of chest through adrenals or PET CT 	X 		Q 12 weeks during Tx 		X 
CT or MRI Brain 	Х				
TREATMENT EXPOSURE (Arm1)- treatment window +/- 3	days				
Nivolumab 480mg Q4W			$X^{13}$		
CORRELATIVE STUDIES					
Mandatory Unstained Slides for Analyses, if available 	Z	K			
Mandatory Whole Blood for Somatic Baseline			Pre C1		
Mandatory Blood, Serum, and Plasma for Analyses 			Pre C1, Pre C2	Х	
Optional Bronchoalveolar Lavage 			X 		•
BANKING SAMPLES					
Optional Whole Blood 			Pre C1, Pre C2	Х	
Optional Unstained Slides 		Х			
Optional Serum and Plasma 			Pre C1, Pre C2	Х	
FOLLOW-UP					
Progression and survival 					Х

#### **Arm 1- Key to Footnotes**

- 1. Medical history to include demographics, trial awareness question, smoking history, prior treatments, radiation and surgical history. Smoking history to include: amount, frequency, start and stop dates of cigarette, cigar and pipe usage. If subject has prior genetic sequencing analyses results available, those results should be submitted by end of Cycle 1.
- 2. Treatment-related adverse events will be followed until resolution, return to baseline, or deemed clinically insignificant. Adverse events (from time of consent) and concomitant medications (28 days prior to start of protocol treatment) should be assessed and recorded until 100 days after last dose of study drug. SAE's and the conmeds used to treat them will be collected up to 100 days post treatment.
- 3. Collection of radiation treatment plan data can take place any time during the study. Data such as total lung volume, V20, and additional radiation parameters will be collected. See Documents/Info tab of the EDC. This data will be recorded in the database for future analysis, but it will not affect treatment while on study and is not required to be collected prior to enrollment or initiation of treatment.
- 4. C1D1 testing does not need to be repeated if performed within 7 days of starting protocol therapy.
- 5. Measured or calculated creatinine clearance (GFR can also be used in place of creatinine or CrCl). Erythrocyte Sedimentation Rate (ESR); C-Reactive Protein (CRP); von Willebrand Factor antigen (vWF Ag). Collect ESR, CRP, vWF and ferritin pre-treatment on C1D1, C2D1 and either at the End of Treatment or if the subject develops any grade 3-4 pneumonitis.
- 6. Thyroid function testing: Perform TSH, T3, T4 at baseline and at odd cycles starting at cycle 3 (i.e. Q 8 wks). T3, T4: free/ total as per local standards.
- 7. For women of childbearing potential. Must have negative pregnancy test within 7 days of registration. Women < 62 yrs old must have FSH > 40 mIU/mL to be considered post-menopausal.
- 8. A pathology report confirming the diagnosis of NSCLC must be obtained and reviewed by the treating physician prior to registration to study.
- 9. All patients require Chest CT through adrenals or PET-CT at the time of screening and at subsequent imaging time points. Abdomen or pelvic CTs or bone scans can be included at the discretion of the treating physician should it be clinically indicated, but these are not mandatory.
- 10. Screening scan including at least CT portion of the chest and abdomen must be performed within 56 days after the completion of chemoradiation or consolidation. PET CT may be done in place of regular CT scans at the discretion of the site investigator. Baseline scans should be done within 28 days prior to treatment initiation. Radiographic disease assessment will be done every 12 weeks ± 4 weeks during study treatment. The scan interval may be reset if scans were done early for clinical reasons. See also 8.3.
- 11. After completion of protocol therapy, subjects who discontinue for reasons other than progressive disease will have post-treatment follow-up for disease status until disease progression, initiating a non-study cancer treatment, withdrawing consent or becoming lost to follow-up. Post treatment radiographic disease assessment should be performed every 3 months until progression. After documented disease progression each subject will be followed for survival every 3 months for up to 2 years, withdrawal of consent, or the end of the study (whichever occurs first).
- 12. A head MRI or CT should be done prior to study treatment for subjects that are symptomatic or have not had prior brain imaging.
- 13. For subjects who meet all eligibility criteria and have recovered sufficiently from treatment with chemoradiation, initial consolidation therapy with nivolumab will be started within 56 days after chemoradiation is complete. For subjects who meet all eligibility criteria after completion of up to two consolidation chemotherapy treatments, therapy with nivolumab will be started within 56 days after last cycle of chemotherapy.
- 14. Mandatory submission of unstained slides from an archived tumor block (if available) for PD-L1, CD4, CD8 by IHC. In addition, whole exome sequencing, RNA sequencing, methylation analysis will be performed. See Correlative Laboratory Manual (CLM) for collection, labeling and shipping instructions.
- 15. Mandatory blood samples for correlative testing should be drawn pre-treatment on C1D1, C2D1 and either at the End of Treatment Visit or if the subject develops any grade 3-4 pneumonitis. See CLM for collection, labeling, and shipping instructions.
- 16. If subject has a bronchoscopy with BAL for clinical reasons, please collect a portion of the of BAL fluid for correlative analysis (optional).
- 17. Optional submission of whole blood for banking is to be collected at Pre-Treatment C1D1, C2D1, and End of Treatment Visit. See CLM for collection, processing, labeling and shipping instructions.
- 18. Optional submission of unstained slides for banking from an archived FFPE tumor block is requested. See CLM for collection, labeling, and shipping instructions.
- 19. Optional submission of serum and plasma for banking are to be collected at Pre-Treatment C1D1, C2D1, and End of Treatment Visit. See CLM for collection, labeling, processing, and shipping instructions.

